9.2.2 Drug Induced Liver Injury (DILI)

Total bilirubin level should be checked for any subject with increased ALT or AST levels \geq three times the upper normal limits (ULN) or baseline.

- Reporting all DILI as SAE to the FDA based on Hy's Law:
 - AST or ALT $\geq 3 \times$ ULN or baseline and
 - T_Bili $\geq 2 \times$ ULN or baseline

A separate incidence table will be provided for DILI cases, and the corresponding listing will be provided for Safety Sample during the double-blind treatment period and the single-blind placebo run-in period.

SAP 405-201-00013

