5.6 Potential Serious Hepatotoxicity

For a subject who experiences an elevation in aspartate aminotransferase (AST) or alanine aminotransferase (ALT) that is ≥ 3 times the upper limit of normal (ULN), a total bilirubin level should also be evaluated. If the total bilirubin is ≥ 2 times the ULN, complete an IRE form with all values listed and also report as an AE on the eCRF.

Protocol 405-201-00013

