7.1 Baseline Definition

Baseline for the single-blind placebo run-in period refers to last available measurement prior to the start of administration of placebo in the single-blind placebo run-in period.

For analyses of the double-blind treatment period data, the baseline is defined as the last available measurement prior to the first dose of double-blind Investigational Medicinal Product (IMP) in the double-blind treatment period.

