Appendix 2 Criteria for Identifying Laboratory Values of Potential Clinical Relevance

Laboratory Tests	Criteria
Chemistry	
AST (SGOT)	≥ 3 x upper limit of normal (ULN)
ALT (SGPT)	≥ 3 x ULN
Alkaline phosphatase	≥ 3 x ULN
BUN	≥ 30 mg/dL
Creatinine	≥ 2.0 mg/dL
Uric Acid	
Men	≥ 10.5 mg/dL
Women	≥ 8.5 mg/dL
Bilirubin (total)	≥ 2.0 mg/dL
Creatine Phosphokinase (CPK)	> 3 x ULN
Hematology	
Hematocrit	
Men	≤ 37 % and decrease of ≥ 3 percentage points from Baseline
Women	≤ 32 % and decrease of ≥ 3 percentage points from Baseline
Hemoglobin	
Men	≤ 11.5 g/dL
Women	≤ 9.5 g/dL
White blood count	≤ 2,800/ mm ³ or ≥ 16,000/ mm ³
Eosinophils	≥ 10%
Neutrophils	≤ 15%
Absolute neutrophil count	≤ 1,500/ mm ³
Platelet count	≤ 75,000/ mm ³ or ≥ 700,000/ mm ³
Urinalysis	
Protein	Increase of ≥ 2 units
Glucose	Increase of ≥ 2 units
Additional Criteria	
Chloride	≤ 90 mEq/L or ≥ 118 mEq/L
Potassium	≤ 2.5 mEq/L or ≥ 6.5 mEq/L
Sodium	≤ 126 mEq/L or ≥ 156 mEq/L
Calcium	≤ 8.2 mg/dL or ≥ 12 mg/dL
Glucose	
Fasting	≥ 100 mg/dL
Non-Fasting	≥ 200 mg/dL
Total Cholesterol, Fasting	≥ 240 mg/dL
LDL Cholesterol, Fasting	≥ 160 mg/dL
HDL Cholesterol, Fasting	
Men	< 40 mg/dL
Women	< 50 mg/dL
Triglycerides, Fasting	≥ 150 mg/dL

SAP 405-201-00013

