- CT-8.7.3 Listing of Treatment-Emergent Adverse Events of Special Interests (AESIs) During the Double-Blind Treatment Period (Safety Sample)
- CT-8.8.1 Incidence of Treatment-Emergent Abuse Potential-Related Adverse Events During the Double-Blind Treatment Period by System Organ Class and MedDRA Preferred Term (Safety Sample)

SAP 405-201-00013

- CT-8.8.2 Incidence of Treatment-Emergent Abuse Potential-Related Adverse Events During the Double-Blind Treatment Period by System Organ Class and MedDRA Preferred Term and Severity (Safety Sample)
- CT-8.8.3 Listing of Treatment-Emergent Abuse Potential-Related Adverse Events During the Double-Blind Treatment Period (Safety Sample)
- CT-9.1.1 Listing of Deaths During the Double-Blind Treatment Period
- CT-9.1.2 Listing of Deaths During the Single-Blind Placebo Run-in Period
- CT-9.2.1 Listing of Serious Adverse Events During the Double-Blind Treatment Period
- CT-9.2.2 Listing of Serious Adverse Events During the Single-Blind Placebo Run-in Period
- CT-9.3 Listing of Discontinuations of Study Medication Due to Adverse Events During the Double-Blind Treatment Period
- CT-9.4 Listing of Adverse Events for Subjects Discontinued from Study Due to Adverse Events During the Double-Blind Treatment Period
- CT-10.1 Criteria for Laboratory Test Values with Potential Clinical Relevance
 - CT-10.2.1.1 Listing of Laboratory Test Values with Potential Clinical Relevance During the Double-Blind Treatment Period by Subject (Safety Sample)
 - CT-10.2.1.2 Listing of Laboratory Test Values with Potential Clinical Relevance During the Double-Blind Treatment Period by Test (Safety Sample)
 - CT-10.2.2 Incidence of Laboratory Test Values with Potential Clinical Relevance During the Double-Blind Treatment Period (Safety Sample)
 - CT-10.2.3.1 Mean Change from Baseline of the Double-Blind Treatment Period in Clinical Laboratory Test Results - Serum Chemistry (Safety Sample)
 - CT-10.2.3.2 Mean Change from Baseline of the Double-Blind Treatment Period in Clinical Laboratory Test Results - Hematology (Safety Sample)
 - CT-10.2.3.3 Mean Change from Baseline of the Double-Blind Treatment Period in Clinical Laboratory Test Results - Urinalysis (Safety Sample)
 - CT-10.3.1.1 Listing of Laboratory Test Values with Potential Clinical Relevance During the Single-Blind Placebo Run-in Period by Subject (Safety Sample)

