 - CT-10.3.1.2 Listing of Laboratory Test Values with Potential Clinical Relevance During the Single-Blind Placebo Run-in Period by Test (Safety Sample)
 - CT-10.3.2 Incidence of Laboratory Test Values with Potential Clinical Relevance During the Single-Blind Placebo Run-in Period (Safety Sample)
 - CT-10.3.3.1 Mean Change from Baseline of the Single-Blind Placebo Run-in Period in Clinical Laboratory Test Results During the Single-Blind Placebo Run-in Period - Serum Chemistry (Safety Sample)
 - CT-10.3.3.2 Mean Change from Baseline of the Single-Blind Placebo Run-in Period in Clinical Laboratory Test Results During the Single-Blind Placebo Run-in Period - Hematology (Safety Sample)
 - CT-10.3.3.3 Mean Change from Baseline of the Single-Blind Placebo Run-in Period in Clinical Laboratory Test Results During the Single-Blind Placebo Run-in Period - Urinalysis (Safety Sample)
 - CT-10.4.1 Incidence of Potentially Liver Injury Related Laboratory Test Abnormalities During the Double-Blind Treatment Period (Safety Sample)
 - CT-10.4.2 Incidence of Potentially Liver Injury Related Laboratory Test Abnormalities During the Single-Blind Placebo Run-in Period (Safety Sample)
 - CT-10.5.1 Listing of Potentially Liver Injury Related Laboratory Test Abnormalities During the Double-Blind Treatment Period (Safety Sample)
 - CT-10.5.2 Listing of Potentially Liver Injury Related Laboratory Test Abnormalities During the Single-Blind Placebo Run-in Period (Safety Sample)
- CT-11.1 Criteria for Potentially Clinically Relevant Abnormalities in Vital Signs
 - CT-11.2.1 Listing of Potentially Clinically Relevant Abnormalities in Vital Signs During the Double-Blind Treatment Period (Safety Sample)

SAP 405-201-00013

- CT-11.2.2 Incidence of Potentially Clinically Relevant Abnormalities in Vital Signs During the Double-Blind Treatment Period (Safety Sample)
- CT-11.2.3 Mean Change from Baseline of the Double-Blind Treatment Period in Vital Signs During the Double-Blind Treatment Period (Safety Sample)
- CT-11.3.1 Listing of Potentially Clinically Relevant Abnormalities in Vital Signs During the Single-Blind Placebo Run-in Period (Safety Sample)
- CT-11.3.2 Incidence of Potentially Clinically Relevant Abnormalities in Vital Signs During the Single-Blind Placebo Run-in Period (Safety Sample)
- CT-11.3.3 Mean Change from Baseline of the Single-Blind Placebo Run-in Period in Vital Signs During the Single-Blind Placebo Run-in Period (Safety Sample)

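### SAP 9.2.2 adds *or baseline* to both limbs of its Hy's Law rule, so its DILI count can include subjects who do not meet the ULN-only rule of protocol 5.6

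*SAP*

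**What the plan says.** SAP 9.2.2 asks for a total bilirubin check when ALT or AST reaches "three times the upper normal limits (ULN) or baseline". It then gives a two-limb rule under the name Hy's Law: AST or ALT at least 3 times ULN or baseline, and total bilirubin at least 2 times ULN or baseline. The output follows from that rule: "A separate incidence table will be provided for DILI cases", with a matching listing, for the Safety Sample in the run-in and double-blind periods.

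Protocol 5.6 (Potential Serious Hepatotoxicity) has the same multipliers but no baseline alternative. AST or ALT of at least 3 x ULN prompts a bilirubin test, and then: "If the total bilirubin is ≥ 2 times the ULN, complete an IRE form", together with an adverse event entry. SAP Appendix 2 also flags AST and ALT against ULN alone; its bilirubin flag is a fixed 2.0 mg/dL. Neither document explains why SAP 9.2.2 adds baseline.

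**The concern.** The usual reason for a baseline multiple in a liver rule is a subject who enters with raised values. Joined to ULN by a plain *or*, it does nothing for that subject: the ULN multiple is reached first. It changes the result only for subjects who start below ULN, where a tripling of enzymes or a doubling of bilirubin need not leave the normal range. The bilirubin limb is there to separate an isolated enzyme rise from one with impaired liver function, and a doubling within normal limits does not show that.

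Liver-injury counts are read at very small numbers, so one added case can change how the table reads. The wording also leaves room for a second programming choice that errs in the opposite direction.

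**Working it through.** The plan states no figure here to reproduce, so the check compares the two rules.

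**Inputs.** The multipliers are 3 (AST/ALT) and 2 (bilirubin), the same in protocol 5.6 and SAP 9.2.2. Baseline for double-blind data is given in SAP 7.1: "the baseline is defined as the last available measurement prior to the first dose of double-blind" study drug. The documents give no ULNs, so I assume enzyme ULNs of 30, 40 and 55 U/L and bilirubin ULNs of 1.0, 1.2 and 1.3 mg/dL.

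**Thresholds.** Let b = baseline/ULN. In multiples of ULN:

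| Limb | Protocol 5.6 | SAP 9.2.2, inclusive *or* | SAP 9.2.2, baseline replaces ULN when raised |
|---|---|---|---|
| AST/ALT | 3 | min(3, 3b) | max(3, 3b) |
| Bilirubin | 2 | min(2, 2b) | max(2, 2b) |

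**Inclusive reading.** For b ≥ 1 the SAP and protocol thresholds are equal; for b < 1 the SAP threshold is lower. Each SAP limb therefore contains the matching protocol limb. A grid with baseline from 0.2 to 2.0 x ULN and on-treatment value from 0.2 to 8.0 x ULN, in steps of 0.05, confirms this:

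- Cells meeting the SAP limb but not the protocol limb: 408 for enzymes and 272 for bilirubin. Of these, 18 and 49 have an on-treatment value at or below ULN.
- Cells meeting the protocol limb but not the SAP limb: 0 and 0.

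These are grid cells, not expected patients.

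*Mixed case.* ALT is at 3 x ULN (90, 120 or 165 U/L) and bilirubin goes from 0.4 to 0.8 mg/dL.

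- Against baseline: 0.8/0.4 = 2.0, so the SAP bilirubin limb is met.
- Against ULN: 0.8/1.0 = 0.80, 0.8/1.2 = 0.67, 0.8/1.3 = 0.62.
- Protocol 5.6 would need 2.0, 2.4 or 2.6 mg/dL and is not met.

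*Enzyme limb alone.* A baseline of 20 U/L gives an SAP threshold of 3 x 20 = 60 U/L. That is 60/30 = 2.00, 60/40 = 1.50 or 60/55 = 1.09 x ULN, against 90, 120 and 165 U/L in the protocol.

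*All values normal.* This needs an enzyme baseline of at most ULN/3 (10.0, 13.3, 18.3 U/L) and a bilirubin baseline of at most ULN/2 (0.50, 0.60, 0.65 mg/dL). One instance, at ULNs of 40 U/L and 1.2 mg/dL, is ALT 12 to 36 U/L with bilirubin 0.3 to 0.6 mg/dL: 36/12 = 3 and 0.6/0.3 = 2. It is an extreme case.

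**Replacement reading.** Take the same ULNs, ALT 72 to 130 U/L and bilirubin 0.6 to 2.5 mg/dL.

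- Protocol 5.6 is met: 130 ≥ 120 and 2.5 ≥ 2.4.
- The replacement rule needs ALT of at least 3 x 72 = 216 U/L and is not met, so a protocol case is lost.
- On the grid, 630 enzyme and 420 bilirubin cells meet the protocol limb but not this one. The mixed and all-normal examples are not counted under this reading.

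**Recovery.** Appendix 2 flags AST or ALT at 3 x ULN and bilirubin at 2.0 mg/dL. Since 2.0 ≤ 2.0, 2.4 and 2.6, every protocol 5.6 case carries both flags in the by-subject listing CT-10.2.1.1 at the assumed ULNs. This needs a bilirubin ULN of at least 1.0 mg/dL, and it yields a listing to read through, not a combined count.

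**The case against.** The best defence is that protocol 5.6 is a site reporting rule, while protocol 7.5 and 7.5.2 leave safety-analysis detail and laboratory criteria to the SAP. A broader analysis screen is then permitted. That stands, and a reader should not infer that the SAP breaches the protocol merely by differing from it. It does not make a baseline multiple within the normal range a Hy's Law finding, which is the name SAP 9.2.2 gives it.

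A reader might also infer that the outputs will be headed Hy's Law. The documents do not show this. The titles of CT-10.4 and CT-10.5 in SAP Section 13 speak of laboratory abnormalities potentially related to liver injury. The shells are not included and may already separate the components. The case-count problem rests on the text of SAP 9.2.2, which promises a table of DILI cases.

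Two further inferences go too far. One is that no protocol case can ever be lost: this holds only on the inclusive reading. The other is that normal values would be sent to the regulator as serious events, because of the sentence beginning "Reporting all DILI as SAE to the FDA based on". Protocol 5.6 governs site reporting and asks for an immediately reportable event form and an adverse event entry, so that sentence is a wording matter.

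It is also fair to say that the outputs are descriptive, that the same rule applies in every arm, and that the promised listing lets each added case be examined. These points limit the harm, but a listing does not correct the count in the table.

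**Conclusion.** The inconsistency is real and should be corrected. On the inclusive reading, SAP 9.2.2 can count as DILI cases subjects who do not meet protocol 5.6, and it loses none who do. On the replacement reading, protocol cases can be lost. A pre-specified liver rule should not depend on which reading is programmed.

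The size is modest. Only a descriptive safety table and its listing are affected; efficacy, alpha and power are not. The number of added cases cannot be estimated from the documents and may be zero. The worked examples rest on assumed ULNs and constructed subjects: they show that the rule can miscount, not that it will.

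**What to change.** Delete *or baseline* from the bilirubin-check trigger and from both limbs of SAP 9.2.2. Cases counted as Hy's Law or DILI in CT-10.4 and CT-10.5 then need AST or ALT ≥ 3 x ULN and total bilirubin ≥ 2 x ULN, as in protocol 5.6. With that change the two threshold rules coincide.

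If a baseline-multiple screen is wanted, show it separately, state its reference rule, and do not label it Hy's Law or DILI. Restricting it to subjects with baseline above ULN would add little: if baseline replaces ULN there, the thresholds exceed the protocol's and the row shows only a subset of protocol cases. As optional tidying, bring the regulator-reporting sentence into line with protocol 5.6.

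The cost is a wording change in the SAP, plus one labelled row or table if the separate screen is kept. No new data are needed.

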9.2.3 Clinical Laboratory Tests in the Single-blind Placebo Run-in Period

Potentially clinically relevant laboratory measurement test results in the Single-blind Placebo Run-in Period will be summarized for the Safety Sample by treatment group and overall as well as listed by subject and by laboratory test.

9.3 Vital Signs

Summary statistics for vital signs will be provided. For the double-blind treatment period vital signs, change from baseline for the double-blind treatment period will be summarized for the Safety Sample by treatment group. Potentially clinically relevant results in vital signs will also be summarized. Similar summaries will be provided for the Safety Sample during the Single-blind Placebo Run-in Period.

9.3.1 Vital Signs in the Double-Blind Treatment Period

Potentially clinically relevant vital signs measurements identified in the double-blind treatment period for the Safety Sample will be summarized by treatment group. Criteria for identifying vital signs of potential clinical relevance are provided in [Appendix 1](#). All potentially clinically relevant events or changes will be listed and included in summary tables.

9.3.2 Vital Signs in the Single-blind Placebo Run-in Period

Potentially clinically relevant vital signs measurements identified in the Single-blind Placebo Run-in Period for the Safety Sample will be summarized by treatment group.

9.4 Electrocardiogram (ECG) Data

Summary statistics and incidence of potentially clinically relevant changes will be provided for ECG parameters.

For the analysis of QT and QTc, data from three consecutive complexes (representing three consecutive heart beats) will be measured to determine average values. The following QT corrections will be used for reporting purposes in the clinical study report:

- 1) QTcB is the length of the QT interval corrected for heart rate by the Bazett formula:
$$QTcB = QT / (RR)^{0.5}$$
 and
- 2) QTcF is the length of the QT interval corrected for heart rate by the Fridericia formula:
$$QTcF = QT / (RR)^{0.33}$$
- 3) QTcN is the length of the QT interval corrected for heart rate by the FDA Neuropharm Division formula: $QTcN = QT / (RR)^{0.37}$

SAP 405-201-00013

9.4.1 ECG Data in the Double-Blind Treatment Period

Potentially clinically relevant changes in the 12-lead ECG identified in the double-blind treatment period for the Safety Sample will be listed and summarized by treatment group. Criteria for identifying ECG measurements of potential clinical relevance are provided in [Appendix 3](#).

Categorical changes in ECG parameters during the double-blind treatment period will be summarized based on the following criteria:

Categorical Change Criteria in QT/QTc Parameters		
Classification	Category	Criteria
QT	New Onset (> 450 Msec)	New onset (>450 msec) in QT means a subject who attains a value > 450 msec during treatment period but not at baseline.
QTc *	New Onset (> 450 Msec)	New onset (> 450 msec) in QTc means a subject who attains a value > 450 msec during treatment period but not at baseline.
	New Onset (> 450 Msec) And > 10% Increase	New onset (> 450 msec) and > 10% increase in QTc means a subject who attains a value > 450 msec and > 10% increase during treatment period but not at baseline
	New Onset (> 500 Msec)	New onset (> 500 msec) in QTc means a subject who attains a value > 500 msec during treatment period but not at baseline.
	Increase 30 - 60 Msec	Increase from baseline value > 30 and ≤ 60 msec in QTc
	Increase > 60 Msec	Increase from baseline value > 60 msec in QTc

* QTc categorical change criteria apply to QTcB, QTcF and QTcN.

9.4.2 ECG Data in the Single-blind Placebo Run-in Period

Potentially clinically relevant changes in the 12-lead ECG identified in the Single-blind Placebo Run-in Period for the Safety Sample will be listed and summarized by treatment group.

9.5 Physical Examinations

By-patient listings will be provided for physical examination.

9.5.1 Body Weight, Waist Circumference and Body Mass Index (BMI)

Analyses of body weight, waist circumference and BMI will be performed for the Safety Sample. The mean change from baseline of the double-blind treatment period to Day 42 (OC) and last visit in the double-blind treatment period in body weight will be tabulated and analyzed using ANCOVA. The ANCOVA models for both the OC and last visit analyses will

SAP 405-201-00013

include the baseline of the double-blind treatment period body weight and the treatment group.

Percentages of patients showing significant weight gain ($\geq 7\%$ increase in weight), as well as percentages of patients showing significant weight loss ($\geq 7\%$ decrease in weight) baseline of the double-blind treatment period to Day 42 (OC and LOCF) will be analyzed using Cochran-Mantel-Haenszel (CMH) General Association Test.

Body mass index is defined as weight in kilograms divided by the square of height in meters.

9.6 Suicidality Data

Suicidality will be monitored during the study using the C-SSRS and will be summarized as number and percentage of subjects reporting any suicidal behavior, ideation, behavior by type (4 types), ideation by type (5 types) and treatment emergent suicidal behavior and ideation. Summary will be provided for the single-blind placebo run-in period and the double-blind treatment period for the Safety Sample.

Suicidality is defined as report of at least one occurrence of any type of suicidal ideation or at least one occurrence of any type of suicidal behavior during assessment period (count each person only once).

Treatment emergent suicidal behavior and ideation is summarized by four types: Emergence of suicidal ideation, Emergence of serious suicidal ideation, Worsening of suicidal ideation, Emergence of suicidal behavior.

Emergence of suicidal behavior/ideation is defined as report of any type of suicidal behavior/ideation during treatment when there was no baseline suicidal behavior/ideation.

Emergence of serious suicidal ideation is defined as observation of suicidal ideation severity rating of 4 or 5 during treatment when there was no baseline suicidal ideation.

Worsening of suicidal ideation is defined as a suicidal ideation severity rating that is more severe than it was at baseline.

For the double-blind treatment period analyses, the last available measurement prior to the first dose of double-blind IMP is being used as “Baseline”.

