6.	Subject has a current comorbid psychiatric disorder that either could be expected to require treatment with medications prohibited in this trial, or to confound efficacy or safety assessments. Examples include, but are not limited to, psychotic disorder (current or lifetime), bipolar disorder (current or lifetime), generalized anxiety disorder, obsessive-compulsive disorder, panic disorder, a current major depressive episode, or posttraumatic stress disorder, as established by the MINI.
7.	Subjects with a clinically significant current DSM-5 diagnosis of borderline, antisocial, paranoid, schizoid, schizotypal, histrionic, narcissistic, avoidant, or dependent personality disorders.
8.	Subjects who meet criteria for C-SSRS Suicidal Ideation Items 4 or 5 within the last 6 months prior to screening or subjects who meet criteria for any of the 5 C-SSRS Suicidal Behavior Items (actual attempt, interrupted attempt, aborted attempt, preparatory acts, or behavior) and whose most recent episode meeting criteria for any of these 5 C-SSRS Suicidal Behavior Items occurred within the last 2 years prior to screening, OR Subjects who, in the opinion of the investigator, present a serious risk of suicide.
9.	Subject has any medical or psychological condition(s) or state(s) that in the investigator's opinion would prohibit the subject from completing the trial or would go against the subject's best interest with his/her participation in the trial. This would include any significant illness or unstable medical condition that could lead to difficulty complying with the protocol. This would also include most bariatric surgeries, with the only exception being those where there has been no breach of the gastrointestinal wall (ie, uncomplicated lap band surgery) AND no sign of malabsorption.
10.	Subject has a history of epilepsy, seizures (other than infantile febrile seizures), syncope, Tourette's Disorder, serious neurological disease, history of significant head trauma with clinically significant loss of consciousness, dementia, cerebrovascular disease, Parkinson's disease, or intracranial lesions.

Protocol 405-201-00013

Table 3.4.3-1 Exclusion Criteria	
11.	Subject has a life-time history of a pattern of abuse or diversion of stimulants.
12.	Subject has any current or suspected drug or alcohol use disorder. Subject has met the DSM-5 criteria for a substance use disorder in the past 6 months. Nicotine use disorder is not exclusionary.

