- CT-14.1.3 Columbia-Suicide Severity Rating Scale(C-SSRS) During the Double-Blind Treatment Period, Suicidal Ideation by Type (Safety Sample)
- CT-14.1.4 Columbia-Suicide Severity Rating Scale(C-SSRS) During the Double-Blind Treatment Period, Treatment Emergent Suicidal Behavior and Ideation (Safety Sample)
- CT-14.1.5 Columbia-Suicide Severity Rating Scale (C-SSRS) – Listing of Treatment Emergent Suicidal Ideation During the Double-Blind Treatment Period (Safety Sample)

SAP 405-201-00013

- CT-14.1.6 Columbia-Suicide Severity Rating Scale (C-SSRS) – Listing of Treatment Emergent Suicidal Behavior During the Double-Blind Treatment Period (Safety Sample)
- CT-14.1.7 Columbia-Suicide Severity Rating Scale (C-SSRS) – Listing of Treatment Emergent Serious Suicidal Ideation During the Double-Blind Treatment Period (Safety Sample)
- CT-14.1.8 Columbia-Suicide Severity Rating Scale (C-SSRS) – Listing of Worsening Suicidal Ideation During the Double-Blind Treatment Period (Safety Sample)
- CT-14.2.1 Columbia-Suicide Severity Rating Scale (C-SSRS) During the Single-Blind Placebo Run-in Period, Suicidality (Safety Sample)
- CT-14.2.2 Columbia-Suicide Severity Rating Scale (C-SSRS) During the Single-Blind Placebo Run-in Period, Suicidal Behavior by Type (Safety Sample)
- CT-14.2.3 Columbia-Suicide Severity Rating Scale (C-SSRS) During the Single-Blind Placebo Run-in Period, Suicidal Ideation by Type (Safety Sample)
- CT-14.2.4 Columbia-Suicide Severity Rating Scale (C-SSRS) During the Single-Blind Placebo Run-in Period, Treatment Emergent Suicidal Behavior and Ideation (Safety Sample)
- CT-14.2.5 Columbia-Suicide Severity Rating Scale (C-SSRS) – Listing of Treatment Emergent Suicidal Ideation During the Single-Blind Placebo Run-in Period (Safety Sample)
- CT-14.2.6 Columbia-Suicide Severity Rating Scale (C-SSRS) – Listing of Treatment Emergent Suicidal Behavior During the Single-Blind Placebo Run-in Period (Safety Sample)
- CT-14.2.7 Columbia-Suicide Severity Rating Scale (C-SSRS) – Listing of Treatment Emergent Serious Suicidal Ideation During the Single-Blind Placebo Run-in Period (Safety Sample)
- CT-14.2.8 Columbia-Suicide Severity Rating Scale (C-SSRS) – Listing of Worsening Suicidal Ideation During the Single-Blind Placebo Run-in Period (Safety Sample)
- CT-15 Summary of Mean Study Medication Withdrawal Questionnaire (SMWQ) Total Score During the Double-Blind Treatment Period and Follow-up Period by Study Day (Safety Sample)

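### The SAP's count of emergent serious suicidal ideation leaves out subjects who rise to a rating of 4 or 5 from baseline ideation rated 1 to 3, and no other planned count isolates them (minor)

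*SAP*

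**What the plan says.** SAP 9.6 summarises the C-SSRS in two ways.

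- **By type, without a stated baseline condition:** "behavior by type (4 types), ideation by type (5 types) and treatment emergent suicidal behavior and ideation". Ideation by type in the double-blind period is CT-14.1.3 in SAP Section 13.
- **Treatment-emergent, in four categories:** "Emergence of suicidal ideation, Emergence of serious suicidal ideation, Worsening of suicidal ideation, Emergence of suicidal behavior". These form CT-14.1.4. Serious emergence and worsening each have a by-subject listing, CT-14.1.7 and CT-14.1.8.

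The ideation categories are defined as follows.

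- Emergence: "report of any type of suicidal behavior/ideation during treatment when there was no baseline suicidal behavior/ideation".
- Serious emergence: "suicidal ideation severity rating of 4 or 5 during treatment when there was no baseline suicidal ideation".
- Worsening: "Worsening of suicidal ideation is defined as a suicidal ideation severity rating that is more severe than it was at baseline".

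For the double-blind period, "the last available measurement prior to the first dose of double-blind IMP is being used as" the baseline.

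The rating-based part of exclusion criterion 8 (protocol 3.4.3) covers "Subjects who meet criteria for C-SSRS Suicidal Ideation Items 4 or 5 within the last 6 months prior to screening". The same criterion separately excludes subjects whom the investigator judges to be at serious risk of suicide.

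**The concern.** The word serious refers to ratings 4 and 5, so one would expect the row to show subjects who did not have a serious rating before treatment and do have one on it. The baseline condition is stricter than that: it requires no ideation of any kind. A subject with mild ideation at baseline who moves to 4 or 5 fails it, and fails the any-ideation emergence row for the same reason.

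Suicidality is a named safety endpoint (protocol 3.5.4). Serious ideation is likely to be rare, so one or two subjects placed elsewhere could change how this row reads between arms. The error has one direction: it can lower the row but never raise it.

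**Working it through.** The plan states no figure for this row, so there is nothing to reproduce. The check applies the definitions literally to every possible pair of ratings.

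**Inputs.** Baseline rating *b* and on-treatment rating *t*, each from 0 (none) to 5, give 6 × 6 = 36 pairs. The definitions come from SAP 9.6. The entry condition comes from exclusion criterion 8.

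**Can a subject enter with a rating of 1 to 3?** Yes. The rating-based exclusion names only items 4 and 5. Only the investigator's judgement of serious risk, or another exclusion, would keep such a subject out.

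**Which pairs does each output cover?**

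| Output | Rule | Pairs |
|---|---|---|
| New serious ideation (target) | *b* 0 to 3, *t* 4 or 5 | 4 × 2 = 8 |
| Serious emergence (CT-14.1.4, CT-14.1.7) | *b* = 0, *t* 4 or 5 | 1 × 2 = 2 |
| Left out of that row | *b* 1 to 3, *t* 4 or 5 | 3 × 2 = 6 |
| Worsening (CT-14.1.4, CT-14.1.8) | *t* > *b* | 5 + 4 + 3 + 2 + 1 = 15 |
| Types 4 and 5 in CT-14.1.3 | *t* 4 or 5, any *b* | 6 × 2 = 12 |

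The six pairs left out are 1→4, 1→5, 2→4, 2→5, 3→4 and 3→5. None meets the any-ideation emergence rule, which also needs *b* = 0. All six meet the worsening rule.

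**Does another output isolate them?**

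- *Worsening.* Its 15 pairs are the six above, five rises from zero (on a literal reading) and four other rises (1→2, 1→3, 2→3, 4→5): 6 + 5 + 4 = 15. A move from 3 to 5 counts the same as a move from 1 to 2.
- *CT-14.1.3.* Its 12 pairs are the eight target pairs plus four that start at 4 or 5. SAP 9.6 describes no baseline comparison for it, so the count alone does not show what is new.

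**How large is the affected group?** The screening form is used once, and the form covering the time since the last visit is used afterwards (protocol 3.7.5.5.2). The C-SSRS is scheduled at Day -7 and Day -1 (Table 3.7-1). When a Day -1 rating exists, baseline therefore reflects only about a week. A subject with ideation at screening but none at Day -1 has baseline 0 and can enter the emergence rows normally. The documents give no C-SSRS counts, so no number of subjects can be computed.

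**The case against.** The strongest reply is that SAP 9.6 already reports the signal. CT-14.1.3 includes every subject rated 4 or 5 on treatment. Because criterion 8 bars recent ratings of 4 or 5, few subjects should have a serious baseline, so its type 4 and type 5 counts should be close to the number wanted. The same subjects also have the worsening row and listing CT-14.1.8. The SAP uses emergence consistently to mean none at baseline and worsening for a rise from something, so this is a choice of categories. Widening the serious row would also break the present nesting: a 3→4 subject would count as serious emergence but not as emergence of ideation.

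Most of this stands. A reader might infer that a shift to serious ideation in these subjects would go unreported, or would be visible only under worsening. The documents do not support either inference, because CT-14.1.3, the worsening row and CT-14.1.8 all include the case. Nor do they say that the serious row was meant to hold subjects with baseline ideation. The nesting point is correct, and any change has to deal with it.

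What the reply does not remove is that CT-14.1.3 could show type 4 or 5 reports while the row and listing titled as emergent serious ideation show none. A reader would then have to work through CT-14.1.8 to reconcile them. Whether the definition follows an outside C-SSRS scoring convention cannot be judged from these documents, and it would not change what the row counts.

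**Conclusion.** The point holds as a minor one. The serious-emergence row and its listing omit subjects who move from a baseline rating of 1 to 3 to a rating of 4 or 5. No planned summary count isolates new serious ideation, and this row can only undercount it.

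The 2-of-8 figure counts kinds of move, not subjects or probabilities. The number of subjects is unknown and probably small, given the short look-back of the Day -1 form and the psychiatric and suicide-risk exclusions. The conclusion rests on reading the baseline condition literally, as no ideation at any level; nothing elsewhere in the SAP widens it. Data collection, subject monitoring and the efficacy results are unaffected.

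**What to change.** In SAP 9.6, define serious emergence as a rating of 4 or 5 during treatment when the baseline rating was 0 to 3. Apply this to CT-14.1.4 and CT-14.1.7, and to the run-in equivalents CT-14.2.4 and CT-14.2.7. Footnote that the row is no longer a subset of emergence of suicidal ideation, or show baseline 0 and baseline 1 to 3 as separate sub-rows. Keep the worsening row as it is.

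Alternatively, keep the current row and add a shift table of baseline against maximum on-treatment ideation rating. That leaves the nesting intact and shows every move.

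The cost is a few words in the SAP and one programming condition, or one extra table. No new data are needed. Under the first option, counts in the serious row can only stay the same or rise; the price is that it is no longer nested in the any-ideation row.
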